#### 3.1 Screening, Recruitment and Consenting:

Under the direction of the PI, trained research staff will be available 24/7 to screen and consent subjects according to study protocol. Medical records of all potential subjects with a diagnosis of PPROM will be reviewed and those who satisfy inclusion and exclusion criteria will be approached and a written informed consent will be obtained. A screening log will be used to track all subjects approached for the study. Potential subjects may be patients of the investigators.

Subjects will be enrolled at the time of admission to labor and delivery (L&D) or thereafter. Subjects will be recruited, enrolled and consented in a private room in labor and delivery or antepartum units in order to respect the privacy of potential subjects. Subjects will be given all the time needed in order to fully understand and read the consent forms. All questions will be fully answered. If needed, a certified language interpreter will be available and Spanish consents will be used as appropriate. Women will only be randomized on our labor and delivery or antepartum units when the decision to initiate antibiotics is made, AND they continue to be eligible (using a randomization screen).

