#### 1- Introduction/Background/Purpose:

In the United States, preterm premature rupture of membranes (PPROM) complicates 4% of pregnancies annually. This pregnancy complication is a major contributor to preterm births and results in neonatal morbidity and mortality. Without treatment, 70-80% of women deliver within the 1st week following membrane rupture. Multiple trials have proven that antibiotics given to this population prolong the latency from time of PPROM to delivery, hence reducing maternal and neonatal morbidities.

According to the American College of Obstetrics and Gynecology, the current standard of care for PPROM subjects between the gestational age of 24 weeks and 0 days and 33 weeks and 6 days, is to administer ampicillin 2 gm IV every 6 hours for 48 hours followed by amoxicillin 250 mg orally every 8 hours for 5 days, with erythromycin 250 mg IV every 6 hours for 48 hours followed by 500 mg orally every 8 hours for 5 days. In this regimen, multiple doses of intravenous (IV) and oral (PO) doses of erythromycin are needed to achieve the desired outcome. Erythromycin can cause GI upset and some subjects do not tolerate this regimen over the course of 7 days. In addition, there is a national shortage of erythromycin, and published expert opinion proposed to use a second-generation macrolide (azithromycin) instead of erythromycin. This strategy was adopted nationwide including our maternal center at UTMB since 2014. Compared to erythromycin, advantages of azithromycin include:

- It is taken once orally (due to its long intracellular half-life).
- The entire regimen is much cheaper than the multiple does of erythromycin (23 doses).
- It has less gastrointestinal adverse effects.

As a result, azithromycin is now commonly being used as a substitute for erythromycin on many labor and delivery units around the country.

Despite its common use, there exists no level 1 evidence that azithromycin is equivalent to erythromycin. Haas and colleagues published a retrospective comparison of the two regimens in 2014 and concluded that the substitution of azithromycin for erythromycin in the recommended antibiotic regimen did not impact latency or any other measured maternal or fetal outcomes. This study, however, was limited by its non-randomized retrospective nature. Our objective is to compare the effectiveness of the 2 regimens in prolonging pregnancy after PPROM.

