#### 3.3. Antibiotics Disposal and Administration

Once a subject is consented and randomized, the appropriate antibiotics according to group assignment will be dispensed by the regular hospital pharmacists after order is placed in EPIC (as part of standard procedure at UTMB). Both drugs are standard of care at UTMB. This is a pragmatic/comparative effectiveness of two standard of care therapies. Regular hospital pharmacy currently stores and disposes the drugs and subject's insurance will be responsible for paying for either antibiotic, as any other subject not in the study. Floor nurses will be administering antibiotics. Research staff will be checking medication administration record (MAR) in EPiC for compliance to the research protocol; if an antibiotic is withheld for any reason the staff will inform the PI and report it as a protocol deviation which may potentially affect the integrity of the data for that subject.

The subject will be included in the analysis by intent-to-treat once the assigned antibiotics are dispensed from inpatient pharmacy and sequential number posted on the subject specific randomization form.

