# 12-Potential benefits:

In the background of erythromycin nationwide shortage, this will be the first level 1 trial to show that azithromycin may be equivalent to erythromycin in delaying delivery in patients with PPROM. This study may show for the first time that current alternative practice with azithromycin is as effective as erythromycin but with less adverse effects, less costly and easy administration.

13-**Statistical approach:** Analysis will be performed by intent to treat. Univariable analysis (such as t-test, Mann-Whitney or Chi-square) will be used for descriptive statistics such as patient demographics and assessment of primary outcome. Multivariable logistic analysis will be used to account for potential confounding variables. Sample size was calculated using a noninferiority trial design. Azithromycin will be tested against erythromycin for PPROM. The primary outcome will be the proportion of subjects undelivered

by day 7. For the sample size calculation, it is assumed the proportion undelivered in the erythromycin group would be 70% (pi = 0.7) based on Haas et al study. We considered that a difference in undelivered rate as large as 15% in favor of erythromycin would allow azithromycin to be non-inferior (delta = 0.15). This study will use 80% power to confirm non-inferiority and a one-sided confidence level of 97.5%.

Estimated sample size for two-sample comparison of proportions (non-inferiority)

Null hypothesis: p2 - p1 � delta (inferior), where:

pi (entered in command) is the overall proportion of participants expected to experience the outcome if the treatments are non-inferior, and delta is the smallest change in proportions between groups (p2 - p1) which would still be clinically important.

Alternative hypothesis: p2 - p1 < delta (non-inferior)

Note: a non-inferiority analysis is one-sided.

```
Assumptions:

power = 0.8000

alpha = 0.0250 (one-sided)

pi = 0.7000

delta = 0.1500

estimated required sample size (per group) = 147
```

The total estimated sample size is 294. Assuming 10% loss to follow, this study proposes a total of 324 subjects will be needed to complete the study. The STAT 14 (Dallas, Tx) will be used for statistical computations. This trial will be registered with Clinical Trials Register (Clinicaltrials.gov), before recruitment is initiated and after IRB approval."

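### Erythromycin is described as in national shortage, yet no supply check before randomisation is described, so a stock-out could cause exclusion from, or crossover within, one arm only

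*Combined protocol and SAP*

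**What the plan says.** Section 1 reports that "there is a national shortage of erythromycin, and published expert opinion proposed to use a second-generation macrolide (azithromycin) instead of erythromycin", and adds: "This strategy was adopted nationwide including our maternal center at UTMB since 2014". Section 12 gives the shortage again as the setting of the trial: "In the background of erythromycin nationwide shortage".

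Under Section 4, the erythromycin arm needs intravenous and then oral erythromycin over seven days. The azithromycin arm needs one oral dose of azithromycin.

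Section 3.1 permits randomisation "when the decision to initiate antibiotics is made, AND they continue to be eligible (using a randomization screen". The inclusion and exclusion criteria (Sections 5 and 6), the central block scheme described with the site list, and Section 3.2 contain no condition on drug supply.

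Under Section 3.3, once a woman is consented and randomised, "the appropriate antibiotics according to group assignment will be dispensed by the regular hospital pharmacists". The section says that the hospital pharmacy holds the drugs at present and that both are standard of care at the lead site. Research staff check the medication administration record for compliance, and "if an antibiotic is withheld for any reason the staff will inform the PI and report it as a protocol deviation". A woman enters the intent-to-treat analysis only from the point at which her allocated antibiotics have been dispensed and her sequence number recorded.

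**The concern.** Only one of the two randomised macrolides is described as scarce, and the other is its usual replacement. A supply failure would therefore fall on one arm. Depending on when it happened, it could do one of two things:

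- **Before any dispensing.** On the natural reading of Section 3.3, the woman never enters the analysis. The erythromycin arm loses women after randomisation and the azithromycin arm does not.
- **After a first dispensing**, for example between the intravenous and oral phases. The woman is already in the analysis. If she is switched to azithromycin she still counts as erythromycin, the arms become more alike, and a non-inferiority test becomes easier to pass.

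Both outcomes weaken the randomised comparison. Supply differs from intolerance or a patient's choice because it can be known before allocation, so the problem can be prevented by design.

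**Working it through.** **Exposure to supply.** From Section 4, erythromycin needs 4 × 2 = 8 intravenous doses and 3 × 5 = 15 oral doses, 23 in all, which agrees with the count in Section 1. Azithromycin needs 1.

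**The plan's own figure.** Section 13 gives 70% undelivered at day 7, a margin of 0.15, one-sided alpha of 0.025 and 80% power:

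n per arm = 2 × 0.70 × 0.30 × (1.960 + 0.842)² / 0.15² = 146.5, rounded up to 147.

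This reproduces the stated 147 per group and 294 in total; 294 × 1.10 gives about 324. With 147 analysed per arm, the standard error is √(0.42/147) = 0.0535 and power is Φ(0.15/0.0535 − 1.960) = 80.1%.

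**Assumed input.** The documents give no supply-failure rate. Let c be the share of the erythromycin arm affected, taken as 5%, 10% and 20% for illustration.

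**Route A: exclusion before dispensing.** The erythromycin n becomes 147(1 − c), the azithromycin n stays at 147, and both true rates are 70%. Power = Φ(0.15/√(0.21/n_E + 0.21/147) − 1.960). The calculation treats these exclusions as additional to the 10% allowance for loss to follow-up.

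**Route B: crossover kept in the arm.** The true rates are 70% and 55%, a deficit exactly at the margin. The erythromycin arm's rate becomes 0.70 − 0.15c, so the observable deficit is 0.15(1 − c). False non-inferiority = Φ(0.15c/SE − 1.960). For c = 0.10, SE = √((0.685 × 0.315 + 0.55 × 0.45)/147) = 0.0561, and Φ(0.015/0.0561 − 1.960) = 4.5%.

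| Assumed c | A: erythromycin n | A: power | B: observable deficit (points) | B: false non-inferiority |
|---|---|---|---|---|
| 0 | 147 | 80.1% | 15.0 | 2.5% |
| 5% | 140 | 79.2% | 14.25 | 3.4% |
| 10% | 132 | 77.9% | 13.5 | 4.5% |
| 20% | 118 | 75.4% | 12.0 | 7.7% |

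Two limits apply. Under route A the type I error stays at 2.5% only if exclusion is unrelated to outcome. Stock-outs would cluster by site and period, and the azithromycin women from those sites and periods would remain, so the arms could differ in case mix. The documents allow neither the size nor the direction of that bias to be worked out. Under route B the figures are upper bounds for each c. They treat every switched woman as wholly azithromycin-treated, whereas one switched after the intravenous phase would already have had 8 of her 23 erythromycin doses.

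**The case against.** The strongest reply is that no supply problem is shown. The documents report no stock-out, no rate, no substitution rule and no switch. Section 3.3 says that the pharmacy holds the drugs, and both regimens are called standard of care at the lead site. Section 1 describes national practice and does not say that any participating site lacks erythromycin. The content of the randomisation screen is not shown and some pages are not in the available text, so a check may exist elsewhere. All of this stands, and the size of the effect rests wholly on assumed rates. Even so, the stock statement is a general one, written around the lead site of a multi-site trial. Holding a drug at present does not assure a full course throughout accrual during a shortage that the plan itself names twice.

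A reader might infer that a stock-out leads straight to one-way crossover and an inflated type I error. Section 3.3 does not support that. A woman never dispensed her allocated drug falls outside the analysis, so the direct result is exclusion and lost power. Crossover kept in the arm needs supply to fail after a first dispensing, or the dispensing rule to be read as met by ampicillin alone.

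A reader might also infer that a substituted macrolide would go unreported. That does not hold either. Replacing erythromycin means withholding it, any reason counts, and the administration record is checked for compliance. The only gap is that replacement is not named and no recording of its reason by arm is specified.

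**Conclusion.** The point holds as a preventable, one-sided risk, not as a demonstrated failure. In the available text, a site without erythromycin could randomise a woman to it. What followed would be either exclusion after randomisation from one arm or dilution within that arm. Exclusion costs power: about 1, 2 and 5 percentage points at assumed failure shares of 5%, 10% and 20%, plus a case-mix bias that cannot be sized. Dilution works in favour of non-inferiority, with a false-positive risk of at most about 3.4%, 4.5% and 7.7% against the planned 2.5%. The dilution figures should not be read as the expected result, because the plan's dispensing rule makes exclusion the more direct route. The planned 147 per group is not in question. This is an inexpensive improvement to the randomisation rule.

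**What to change.** Three linked changes:

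1. **Section 3.1, randomisation screen.** Add: *Site pharmacy confirms that both assigned regimens can be supplied for the full course; if not, do not randomise.*
2. **Section 3.3, analysis set.** Analyse all randomised women in the arm to which they were allocated, whether or not the assigned drug was dispensed. This removes one-arm exclusion. Any remaining supply failure would then act through dilution, so this change should go with the supply check.
3. **Section 3.3, deviations.** State that replacement of the assigned macrolide is a reportable deviation, record the reason (supply, intolerance, other), and report the counts by arm.

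What a woman receives if supply fails during treatment is a matter for the investigators and is not addressed here.

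The cost is one line on an existing screen, a pharmacy check and two reworded sentences, with no change in sample size. The downside is that recruitment pauses at a site while it lacks erythromycin, when that site could not deliver the comparison anyway.

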#### 3.2 Randomization

A confidential computer-generated simple randomization scheme (using STATA 14, Dallas, Tx) will be prepared and provided on an ongoing basis to our study coordinator. A randomization log with group assignment, subject name and medical record number will be used to track the randomization process. Across multi-sites, randomization is centralized. UTMB perinatal research division synchronizes randomization assignment schedule by increments of blocks of 10 as enrollment is ongoing.

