# United States, Texas

St. David's North Austin Medical Center Recruiting Austin, Texas, United States, 78758 Contact: [name] [contact] [contact] PI : [name] [contact]

Each center had the protocol reviewed and approved independently by their local IRB before participating in this trial or recruiting.

UTMB is the leading site for this trial. There is no specific accrual number per site. Across multi-sites, randomization is centralized. UTMB perinatal research division coordinates randomization assignment schedule by increments of blocks of 10 as enrollment is ongoing. Each block has 10 subjects randomized to either intervention A or B which is independent and does not affect the remaining sequence. For example, Block #1 has the first 10 subjects, within the block we will have 5 in intervention A and 5 in intervention B randomization independent of the remaining sequence or Block. Each site will be given 1-3 blocks of 10 increments for randomization. This approach is independent of the remaining sequence or blocks, thus not affecting the remaining randomization sequence.

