#### **10-Subject Safety and Data Monitoring:**

The collaborators and research coordinator will be responsible for monitoring the safety of this study. The report will include participant demographics, expected versus actual recruitment rates, summary of any quality assurance or regulatory issues, summary of adverse events (AEs) or serious adverse events (SAEs) which may have occurred, and any changes in the protocol as a result of these issues. This report will be prepared yearly and be sent to the PI's. The collaborators and research coordinator will monitor for adherence to consent procedures, inclusion and exclusion criteria, valid abstraction, correct entry, timeliness and responsiveness to data queries. Data collection will be identified with a participant ID number. Data will be collected and stored with the participant ID code only. The master enrollment log linking subject identifiers with study ID numbers will be kept in a password-protected database. Several data collection forms will be used. Data on these forms devoid of personal identifiers will be securely stored at our perinatal research division. The research coordinator and PIs will be available to monitor the data and correct any discrepancies based on source documents if needed.

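### No allocation concealment is described: blocks of assignments go to sites and the scheme to the coordinator before enrolment, which permits foreknowledge of the next arm in a trial with no described treatment masking

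*Combined protocol and SAP*

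**What the plan says.** Three parts of the plan bear on who can see an assignment, and when.

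- **Who receives the scheme.** Section 3.2 describes a scheme produced by computer, labelled confidential and simple, that "will be prepared and provided on an ongoing basis to our study coordinator". The same section adds "Across multi-sites, randomization is centralized".
- **What sites receive.** The site section (under the Texas heading): "Each site will be given 1-3 blocks of 10 increments for randomization". It also discloses the composition: "within the block we will have 5 in intervention A and 5 in intervention B randomization independent of the remaining sequence or Block".
- **Order of events.** Section 3.1 places randomization after consent, "when the decision to initiate antibiotics is made, AND they continue to be eligible (using a randomization screen". Section 3.2 provides a log of assignment, name and record number. Section 3.3 then brings a woman into the intent-to-treat analysis once the assigned drug has been dispensed and a sequential number posted on her form.

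On roles, section 3.1 says "trained research staff will be available 24/7 to screen and consent subjects according to study protocol", and section 10 says "The collaborators and research coordinator will monitor for adherence to consent procedures, inclusion and exclusion criteria". The only masking described is of the primary-outcome review (section 3.4). The drugs are ordered in the medical record and given by floor nurses (section 3.3).

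**The concern.** A block must reach a site before the women who fill it are enrolled. The plan mentions no sealed envelopes, no web or telephone release and no pharmacy-held list, and it sets no barrier between the list and the people who recruit. If a recruiter can see the next arm, that knowledge can influence whom they approach and when.

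This trial leaves room for such influence. Rupture of membranes is determined clinically, dilation is judged by eye, any contraindication to expectant management excludes, and enrolment may come at admission or later. Some women may be the investigators' own patients. The screening log covers women approached, so a woman who was never approached leaves no trace in it.

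Steering women likely to deliver early away from azithromycin moves the result towards non-inferiority. Steering them away from erythromycin costs power. An intent-to-treat analysis cannot restore women who never entered, and the planned multivariable model can adjust only for recorded factors. Because section 3.3 ties entry to the analysis set to dispensing, a woman can also fall out of the analysis after her arm is known.

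**Working it through.** **1. The plan's own figure.** Inputs from section 13: 70% undelivered in both arms, margin 0.15, one-sided alpha 0.025, power 80%.

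n = 2 × 0.70 × 0.30 × (1.960 + 0.842)² / 0.15² = 146.5, so 147 per group and 294 in total, as stated. 294 × 1.10 = 323.4, rounded up to the stated 324. Concealment does not change the sample size.

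**2. How much can be known in advance.** If a site can read its blocks, 10 of 10 assignments are known. If they are hidden but earlier arms are visible, best guessing in a 5:5 block of 10 gets 5 + (1024/252 − 1)/2 = 6.53 right, against 5 by chance. On average 1.67 of 10 are then certain.

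**3. Illustration of the effect.** None of the following inputs is in the documents. A share s = 20% of eligible women is visibly poor-prognosis, with 35% undelivered at day 7 on erythromycin. A fraction d of them is not enrolled when azithromycin is next, with the same direction of steering throughout.

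- Good-prognosis rate on erythromycin: (0.70 − 0.35 × 0.20)/0.80 = 0.7875.
- Poor-prognosis share left in the azithromycin arm: s′ = s(1 − d)/(1 − sd), which is 0.15/0.95 = 0.158 for d = 25% and 0.10/0.90 = 0.111 for d = 50%.
- Bias = (s − s′) × (good rate − poor rate on azithromycin).

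The true azithromycin rate is set at the margin, 55% overall. The answer depends on how the 15-point deficit is spread over the two prognosis groups, so three versions are shown. False non-inferiority is the exact probability, from two binomials with n = 147 each, that the lower 97.5% Wald limit exceeds −0.15. Without bias it is 2.4%.

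| Spread of the deficit | Azithromycin rates, poor / good | Bias, d = 25% / 50% | False non-inferiority, d = 25% / 50% |
|---|---|---|---|
| 15 points in both groups | 0.20 / 0.6375 | +1.8 / +3.9 points | 5.0% / 10.2% |
| Proportional (55/70) | 0.275 / 0.619 | +1.4 / +3.1 points | 4.3% / 7.7% |
| None in the poor group | 0.35 / 0.60 | +1.1 / +2.2 points | 3.7% / 5.8% |

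With s varied from 10% to 30%, the extremes are 3.0% (s = 10%, d = 25%, third row) and 20.0% (s = 30%, d = 50%, first row).

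**4. The other direction.** With equal true rates of 70%, a shift of 1.8 or 3.9 points against azithromycin (70% becomes 68.2% or 66.1%) cuts power from 80% to 69% or 54%.

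**The case against.** A reader might infer that allocation is simply not concealed and that recruiters know the next arm with certainty. The documents do not support that. The scheme is called confidential and randomization centralized. The form in which blocks reach sites, and who there can see them, is not stated. No section says that the coordinator approaches or consents women; section 10 gives that role monitoring duties. The procedure is under-described, and sealed envelopes could be in use.

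Nor is dispensing the first recorded commitment. Written consent, the eligibility re-check and the randomization log are recorded too, and section 3.3 itself starts from a woman already consented and randomized. Its dispensing rule defines entry to the analysis set, which is a narrower problem.

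The size is also open to challenge: it rests on assumed inputs and consistent one-way steering, and the largest values need a constant 15-point deficit in both prognosis groups.

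These objections limit the claim but do not remove it. Confidential and centralized are labels, and the one distribution step described sends assignments out ahead of enrolment. Placing randomization after consent settles when a woman is assigned, not who already knows the next assignment.

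**Conclusion.** The point holds in this form: no concealment mechanism is described, nothing separates the list holder from recruiting staff, and handing blocks to sites in a trial with no described treatment masking permits foreknowledge and selective enrolment. The dispensing rule in section 3.3 adds a route by which women can leave the analysis after assignment.

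The documents give no basis for the actual size or direction of any bias. On the stated assumptions, false non-inferiority goes from 2.4% to about 4% to 6% or 5% to 10%, depending on how the deficit is spread, and to about 3% to 20% over the wider range. These figures show that modest selection would matter; they do not forecast that it will occur. The change is worth making because it is cheap and closes a route that no later analysis can repair.

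**What to change.** - **Site section and section 3.2.** Do not send readable blocks to sites or to anyone who recruits. Keep the list in the UTMB perinatal research division with a person who does not screen, consent or check eligibility.
- **Release.** Give out one assignment at a time, after the woman's study number, confirmed eligibility and signed consent are logged. Where round-the-clock recruitment makes that impractical, use sequentially numbered, opaque, sealed envelopes, signed and timed before opening and reconciled centrally. If such envelopes are already in use, say so.
- **Section 3.3.** Count every woman in the intent-to-treat set from that assignment, whether or not the drug is dispensed.

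The cost is a short amendment plus a few minutes' delay per randomization or the printing of envelopes. The central office, the Stata list and the 147 per group stay. The documents give no staffing information, so whether a suitable list holder is already available must be confirmed.

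This removes direct sight of the sequence only. With fixed, disclosed 5:5 blocks, about 6.5 of 10 assignments remain guessable, so it would not by itself guarantee the nominal error rate. Block size needs separate attention.
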